7.2.4. Body Surface Area

Total % BSA affected will be estimated at each visit. Body surface area assessment will be approximated to the nearest 0.1% using the Palmar Method as a guide. The Palmar Method is the palm plus 5 digits, with fingers tucked together and thumb tucked to the side (handprint) as 1% BSA and the thumb as 0.1% BSA.

7.2.5. Patient-Reported Outcomes

Patient-reported outcomes will be collected and assessed. For all patient-reported outcome assessments conducted at the study site, in order to avoid bias in the participants' responses to the questionnaires, assessments should be completed before any other evaluations or study procedures on the day of the study visit and prior to treatment-related discussions with the investigator or study site staff.

7.2.5.1. Itch Numerical Rating Scale

The Itch NRS is a daily participant-reported measure (24-hour recall) of the worst level of itch intensity (Kimball et al 2016, Silverberg et al 2021). Participants will be instructed to complete and record their Itch NRS in a diary each evening beginning on the day of screening through Week 24 or treatment discontinuation. Participants will rate itch severity of their LS by selecting a number from 0 (no itch) to 10 (worst imaginable itch) that best describes the worst level of itch they experienced in the past 24 hours.

[figure not shown]
The participant's baseline Itch NRS score will be determined by averaging the 7 daily NRS scores before Day 1 (ie, Days –7 to –1) for all the by-visit summaries. The by-visit Itch NRS score for postbaseline visits will be determined by averaging the 7 daily NRS scores before the visit day. If 4 or more daily scores (out of the 7) are missing, the by-visit Itch NRS score will be set to missing. For all daily itch-related analyses, including time to achieve Itch NRS score improvement of at least 4 points analysis, baseline will be defined as the last available Itch NRS score during the week prior to Day 1 (ie, Days –7 to –1). Nonresponder imputation will be used to handle missing postbaseline values in the DBVC period.

A participant is said to have an ITCH4 response if they achieved a \geq 4-point improvement in Itch NRS score from baseline. For determining ITCH4 response at a visit, the by-visit Itch NRS score will be compared with the baseline Itch NRS score. For the endpoint time to achieve ITCH4, the daily Itch NRS score will be compared with the baseline Itch NRS score.

[figure not shown]

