2.1.1. Scientific Rationale for Study Design

Similar to AD and vitiligo, LS is considered to be an inflammatory dermatosis. Although etiology of LS is unknown, it is considered to be an autoimmune disease with dysregulation of Th1 response. Several cytokines including IL-1, IL-7, IL-15, INF-γ, TNF-α have been implicated in the pathogenesis of LS (Szabo et al 2003, Terlou et al 2012). Additionally, Th1 associated chemokines such as CXCR3 and CCR5, are overexpressed in LS. Similar to AD and vitiligo, JAK1 and JAK2-associated cytokines are involved in the pathogenesis of LS. Ruxolitinib is a selective inhibitor of JAK1 and JAK2 and, based on its demonstrated efficacy in both AD and vitiligo in well-designed pivotal Phase 3 trials, ruxolitinib 1.5% cream is expected to have potential activity in LS.

There is currently no FDA approved treatment of LS. High-potency steroids are the mainstay of treatment; however, their continued use is associated with skin atrophy and other side effects, which limits their use. There are no published studies on topical JAK inhibitors in LS. Prior studies comparing high-potency topical steroids with either topical pimecrolimus (Goldstein et al 2011) or topical tacrolimus (Funaro et al 2014) demonstrate the superiority of high-potency topical steroids. Symptoms (eg, itching or pain) can be partially improved by application of vehicle with up to 75% participants reporting improvement in some studies (Sideri et al 1994). Because of substantial response to vehicle or petroleum ointments, it is crucial to compare ruxolitinib 1.5% cream to vehicle to assess the independent effect of ruxolitinib on LS. For this reason, a random 1:1 allocation design was chosen for this study. Additionally, symptoms of LS may wax and wane and may be exacerbated by sexual or physical activity. Therefore, a 12-week double-blind vehicle-controlled study has been designed, which will allow sufficient length of time to compare ruxolitinib against vehicle and is ethically acceptable. This is in line with prior RCTs in LS, which used a 12-week duration of treatment (Goldstein et al 2011). The proposed study would also assess safety of ruxolitinib 1.5% cream in participants with LS.

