5.1. Inclusion Criteria

Participants are eligible to be included in the study only if all of the following criteria apply:

- 1. Ability to comprehend and willingness to sign a written ICF for the study.
- 2. Females only, aged 18 years or older at screening.
- 3. Biopsy-proven LS in the anogenital area. Total BSA including anogenital and nonanogenital area should not exceed 10% BSA.
 - *Note:* Participants who have newly diagnosed LS, or have LS refractory to prior treatments, or have progressive LS (such as fusion of the labia minora, phimosis of the clitoral hood, and fissures) will be allowed to participate in the study.
- 4. Baseline IGA score > 2 for LS.
- 5. Baseline Itch NRS score ≥ 4 in anogenital area. Baseline Itch NRS score is defined as 7-day average of Itch NRS score before Day 1 (data from a minimum 4 out of 7 days directly prior to Day 1 is needed).

- 6. Participants who agree to discontinue all agents used by the participant to treat LS from the screening visit (according to washout timeline enumerated under exclusion criterion 4; see Section 5.2) through the final safety follow-up visit.
- 7. Willingness to avoid pregnancy based on the criteria below.
 - a. Female participants who are WOCBP must have a negative serum pregnancy test at screening and a negative urine pregnancy test before the first application on Day 1 and must agree to take appropriate precautions to avoid pregnancy from screening through 30 days (1 menstrual cycle) after the last application of study treatment and must refrain from donating oocytes during this period. Permitted methods in preventing pregnancy (see Appendix A) should be communicated to the participants and their understanding confirmed.
 - b. A female participant not considered to be of childbearing potential as defined in Appendix A is eligible.

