8.2.7.1. Diary Assessments: Itch NRS and Skin Pain NRS

The participant will rate the following:

- Itch NRS: The Itch NRS is a daily participant-reported measure (24-hour recall) of the worst level of itch intensity (Kimball et al 2016, Silverberg et al 2021). The participant will be instructed to complete and record the Itch NRS via a diary, daily, in the evening beginning on the day of screening through Week 24 or treatment discontinuation. The participant will rate itch severity of their LS by selecting a number from 0 (no itch) to 10 (worst imaginable itch) that best describes the worst level of itching in the past 24 hours.
- Skin Pain NRS: Pain (includes all types of pain such as feeling of burning, tearing, pulling, stabbing, etc) severity of the LS by selecting a number from 0 (no pain) to 10 (worst imaginable pain) that best describes their worst level of pain in the past 24 hours. The participant will be instructed to complete and record the Pain NRS via a diary, daily, in the evening beginning on the day of screening through Week 24 or treatment discontinuation based on 24-hour recall.

The average of the 7-day Itch NRS score prior to the baseline visit (minimum 4 out of 7 days' data required) will be used to determine if a participant meets inclusion criteria.

In addition, the diary may be used for optional reporting of sexual activity or other activities, which may exacerbate pain or itching. Detailed directions for the administration of a diary will be provided in the Study Manual.

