7.4.2. Time-To-Event Efficacy Endpoint

The time to achieve Itch NRS score improvement of at least 4 points from baseline (ie, ITCH4) will use the daily Itch NRS score in comparison to baseline Itch NRS score in the DBVC period. A log-rank test will be used for between-treatment group comparisons. The hazard ratio and its 95% CI will be estimated based on the Cox regression model using Efron's method accounting for ties. Kaplan-Meier curves will be presented by treatment groups. The number of participants, number of events, and number of censoring will be summarized by treatment groups. The Kaplan-Meier estimate of median time will be presented with its 95% CI. The 95% CI will be calculated using the method by Brookmeyer and Crowley (1982).

The last available value for time to ITCH4 during the DBVC period is the last nonmissing measurement obtained after the first application of study cream and within 30 days after the last application of study cream in DBVC period, or before the first application of study cream in the OLE period, whichever is earlier.

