1.1 Disposi			
1.1.1	Analysis Populations	ITT	X
1.1.2.1	Summary of Participant Disposition in the DBVC Period	ITT	X
1.1.2.2	Summary of Participant Disposition in the OLE Period	OLE	X
1.1.3	Summary of Number of Participants Enrolled by Country and Site	ITT	X
1.1.4.1	Summary of Protocol Deviations in the DBVC Period	ITT	X
1.1.4.2	Summary of Protocol Deviations in the OLE Period	OLE	X
1.2 Demogr	raphics and Baseline Characteristics		
1.2.1	Summary of Demographics and Baseline Characteristics	ITT	X
1.2.2	Summary of Demographics and Baseline Characteristics	OLE	X
1.3 Baselin	e Disease Characteristics		
1.3.1	Summary of Baseline Disease Characteristics	ITT	X
1.3.2	Summary of Baseline Disease Characteristics	OLE	X
1.4 Prior a	nd Concomitant Medication		•
1.4.1	Summary of Prior Medications	ITT	X
1.4.2.1	Summary of Concomitant Medications in the DBVC Period	ITT	X
1.4.2.2	Summary of Concomitant Medications in the OLE Period	OLE	X
1.5 Others			•
1.5	Summary of General Medical History in the DBVC Period	ITT	X
Efficacy			
2.1 Itch NR	RS Score		
2.1.1	Summary and Analysis of Participants Achieving ITCH4 in Treatment Periods	ITT	
2.1.2	Summary and Analysis of Participants Achieving ITCH4 by Baseline ITCH NRS Score in Treatment Periods	ITT	
2.1.3	Summary and Analysis of Participants Achieving ITCH4 by Baseline IGA Score in Treatment Periods	ITT	
2.1.4	Summary and Analysis of Participants Achieving ITCH4 by Baseline Age Group in Treatment Periods	ITT	
2.1.5	Summary and Analysis of Participants Achieving ITCH4 by Baseline Duration of Disease in Treatment Periods	ITT	
2.1.6	Summary and Analysis of Participants Achieving ITCH4 by Childbearing Potential Status in Treatment Periods	ITT	
2.1.7	Summary and Analysis of By-Visit Itch NRS Score in Treatment Periods	ITT	
2.1.8	Summary and Analysis of Daily Itch NRS Score from Day 1 to Day 28	ITT	
2.1.9	Summary and Analysis of Time to ITCH4 in the DBVC Period	ITT	
2.2 CLISSO	· · ·		
2.2.1	Summary and Analysis of CLISSCO Total Score and Subscores in Treatment Periods	ITT	

Table No.	Title	Population	Standard
	nin NRS Score	T	T
2.3.1	Summary and Analysis of By-Visit Skin Pain NRS Score in Treatment Periods	ITT	
	1 erious		
		1	ı
	T	T	1
	 		
			1

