4.1.3.2	Mean and Standard Error Plot of Change From Baseline in Daily Itch NRS Score From Day 1 to Day 28	ITT
4.1.4	Kaplan-Meier Curve of Time to ITCH4 in the DBVC Period	ITT
4.2.1.1	Mean and Standard Error Plot of Total CLISSCO in Treatment Periods	ITT
4.2.1.2	Mean and Standard Error Plot of Change From Baseline in Total CLISSCO in Treatment Periods	ITT
4.2.1.3	Mean and Standard Error Plot of Percentage Change From Baseline in Total CLISSCO Score in Treatment Periods	ITT
4.3.1.1	Mean and Standard Error Plot of By-Visit Skin Pain NRS Score in Treatment Periods	ITT
4.3.1.2	Mean and Standard Error Plot of Change From Baseline in By-Visit Skin Pain NRS Score in Treatment Periods	ITT
4.3.1.3	Mean and Standard Error Plot of Percentage Change From Baseline in By-Visit Skin Pain NRS Score in Treatment Periods	ITT
4.10.1.1	Mean and Standard Error Plot of Total % BSA in Treatment Periods	ITT
4.10.1.2	Mean and Standard Error Plot of Change From Baseline in Total % BSA in Treatment Periods	ITT
4.10.1.3	Mean and Standard Error Plot of Percentage Change From Baseline in Total % BSA in Treatment Periods	ITT

Listings

T	TO A
Listing No.	Title
8 1	phic and Baseline Characteristics
2.1.1	Participant Enrollment and Disposition Status
2.1.2	Participant Inclusion and Exclusion Criteria Violations

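### Time to ITCH4 is measured from one evening's diary score instead of the 7-day average, so some eligible participants can never have an event and the log-rank test may lose power

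*SAP*

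**What the plan says.** Protocol 5.1, criterion 5, requires a baseline itch score of at least 4 and states: "Baseline Itch NRS score is defined as 7-day average of Itch NRS score before Day 1", from at least 4 of the 7 days. SAP 7.2.5.1 uses the same 7-day average as baseline for by-visit scores, including Week 12 ITCH4.

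For daily itch analyses, with time to ITCH4 named, the same SAP section switches: "baseline will be defined as the last available Itch NRS score during the week prior to Day 1". It then says "For the endpoint time to achieve ITCH4, the daily Itch NRS score will be compared with the baseline Itch NRS score". SAP 7.4.2 repeats that the endpoint "will use the daily Itch NRS score in comparison to baseline Itch NRS score in the DBVC period" and has no rule for participants whose last score is below 4. Because the rule covers all daily itch analyses, it also governs two displays in SAP Appendix A: Table 2.1.8 ("Summary and Analysis of Daily Itch NRS Score from Day 1 to Day 28") and Figure 4.1.3.2 ("Mean and Standard Error Plot of Change From Baseline in Daily Itch NRS Score From Day 1 to Day 28").

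Protocol 10.4.2 specifies a log-rank test and a Cox hazard ratio for time to ITCH4 but gives it no separate baseline. SAP 11.1 records no change from the protocol's analyses.

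**The concern.** The plan lets in participants on an averaged score and then measures their time to response from a single score. One pre-treatment evening, unrelated to treatment, affects how far a participant must fall and sometimes whether an event is possible at all. The protocol itself expects fluctuation: "symptoms of LS may wax and wane and may be exacerbated by sexual or physical activity" (Protocol 2.1.1).

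Time to ITCH4 is one of three secondary efficacy endpoints and the only one for which the protocol specifies a between-group test. With about 60 participants and no power calculation, avoidable noise weakens the evidence on whether the cream deserves further study.

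**Working it through.** **1. Arithmetic on the scale (no assumptions).** An event needs a daily score at or below baseline minus 4, and scores run from 0 to 10.

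- Diary 5, 5, 5, 5, 5, 5, 3: mean 33/7 = 4.71, so eligible. From the last score the threshold is 3 - 4 = -1, which is impossible. From the average it is 0.71, so a score of 0 counts.
- Diary 5, 5, 5, 5, 5, 5, 9: mean 39/7 = 5.57. From the last score the threshold is 9 - 4 = 5, so her first usual evening is an event. From the average it is 1.57, so she needs 1 or less.

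**2. Log-rank power.** The plan states no power for any endpoint, so there is no figure to reproduce. From the documents: about 60 participants randomized 1:1 (30 per arm), 12 × 7 = 84 daily scores, eligibility at a 7-day mean of at least 4. The two-sided 0.05 level is stated for the primary analysis only and is assumed here.

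Assumed, because the documents are silent: person mean 6.5 (SD 1.6); AR(1) daily deviations; scores rounded and clipped to 0-10; linear fall to full effect by Day 28; individual fall SD 2.0; no dropout. There were 4,000 simulated trials per cell (standard error at most 0.8 points).

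Cells show power (%) as single-day / averaged baseline, with an event based on the trailing 7-day average in brackets.

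Larger effect (mean falls 4.05 vs 1.8):

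| Autocorrelation | SD 0.5 | SD 1.0 | SD 1.5 | SD 2.0 |
|---|---|---|---|---|
| 0.3 | 95 / 95 (94) | 83 / 94 (94) | 44 / 80 (91) | 18 / 52 (88) |
| 0.7 | 94 / 95 (94) | 84 / 90 (92) | 54 / 77 (87) | 27 / 53 (77) |
| 0.9 | 94 / 93 (93) | 88 / 89 (90) | 72 / 79 (83) | 49 / 61 (70) |
| 0.95 | 94 / 94 (93) | 90 / 90 (90) | 78 / 80 (82) | 62 / 67 (72) |

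Smaller effect (mean falls 3.0 vs 1.5):

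| Autocorrelation | SD 0.5 | SD 1.0 | SD 1.5 | SD 2.0 |
|---|---|---|---|---|
| 0.3 | 64 / 64 (58) | 50 / 64 (61) | 25 / 50 (59) | 13 / 31 (54) |
| 0.7 | 63 / 62 (59) | 53 / 61 (59) | 31 / 47 (53) | 18 / 30 (45) |
| 0.9 | 61 / 60 (57) | 54 / 56 (55) | 40 / 46 (46) | 28 / 34 (38) |
| 0.95 | 61 / 59 (57) | 56 / 55 (54) | 46 / 48 (47) | 35 / 38 (39) |

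When the falls are re-solved in each setting to give Week 12 ITCH4 rates of 51% vs 16%, close to the atopic dermatitis itch rates in Protocol 2.1, SD 1.5 gives 45 / 81, 68 / 87, 88 / 92 and 92 / 95 at autocorrelation 0.3, 0.7, 0.9 and 0.95 (2,000 trials each).

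A second simulation with exponential onset (14-day time constant) and mean falls of 3.5 vs 1.5 shows the same pattern: 46 / 72 at SD 1.5, correlation 0.5; 44 / 56 at SD 2.0, correlation 0.9; 84 / 83 at SD 0.75, correlation 0.9.

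**3. Participants unable to have an event** (last score 3 or less), with person mean varied from 5.5 to 7.5:

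| Autocorrelation | SD 0.5 | SD 1.0 | SD 1.5 | SD 2.0 |
|---|---|---|---|---|
| 0.3 | 0-1% | 1-4% | 2-8% | 5-12% |
| 0.9 | 0% | 0-1% | 1-3% | 2-5% |
| 0.95 | 0% | 0-1% | 0-2% | 1-3% |

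The largest share, 12%, is 0.12 × 60, or about 7 participants.

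**4. Influence of the baseline evening** (SD 1.5, no true change). Compare participants whose last day was at least 1 point above their own average with those at least 1 point below. With the single-day baseline, event rates are 95% vs 8% at autocorrelation 0.3 and 62% vs 12% at 0.9. With the averaged baseline they are 34% vs 43% and 19% vs 33%.

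**5. What averaging does not cure.** Chance events with no true change, single-day / averaged (trailing), at SD 1.0, 1.5 and 2.0:

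- autocorrelation 0.3: 16 / 2 (0), 53 / 38 (0), 73 / 75 (3)%
- autocorrelation 0.9: 8 / 3 (1), 36 / 25 (11), 58 / 51 (29)%

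**6. Type I error** with equal falls of 1.8: 4.9-5.9% (single-day), 5.1-6.0% (averaged), 4.4-5.8% (trailing).

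**The case against.** The SAP does not contradict itself. It pairs by-visit scores with an averaged baseline and daily scores with a daily one, in advance, and does the same for skin pain (SAP 7.2.5.2). The trial is unpowered and alpha is stated only for the primary analysis, so this log-rank p-value is nominal. That stands: this is a weak design choice, and it threatens neither error control nor the main conclusion.

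The size is also not fixed by the documents. Protocol 2.1.1 fits both slow drift and brief flares, and the tables run from a 2-point loss under the averaged baseline to a 36-point gain. That stands too, and the power claim is conditional for this reason.

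The averaged baseline softens the floor without removing it. Participants averaging 4 to below 5, about 10 to 14% of those eligible in this model, could have an event only at a score of 0. Nor does it stop one good evening in 84 from counting: at SD 2.0 and autocorrelation 0.3, chance events are no fewer. Both points are right. They argue for adding a trailing-average analysis, and neither is a reason to keep the single-day baseline as the main one.

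**Conclusion.** The concern holds. That an eligible participant may be unable to have an event is exact arithmetic. How many are affected, and how much power is lost, depend on diary variability that the documents do not report.

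Under the stated assumptions, the loss at daily SD 1.5 with the larger effect is 36 points at autocorrelation 0.3 (80 - 44), 23 at 0.7 (77 - 54), 7 at 0.9 (79 - 72) and 2 at 0.95 (80 - 78). There is no material loss at SD 0.5. The primary endpoint and Type I error are unaffected. The change is worth making because it costs little, but the trial does not stand or fall on it. Confidence in the size is medium.

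**What to change.** In SAP 7.2.5.1 and 7.4.2:

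- Use the Days -7 to -1 average, from at least 4 scores, as baseline for time to ITCH4. Keep the daily event, and keep the single-day-baseline analysis as supportive.
- Preferably move Table 2.1.8 and Figure 4.1.3.2 to the same average, so that daily itch has one baseline. At SD 1.5 with no true change, the SD of Day 28 change would then be 1.61 instead of 2.06 at autocorrelation 0.3, and 1.85 instead of 1.97 at 0.9.
- Add a trailing 7-day-average event, with the same minimum of 4 scores, as a planned sensitivity analysis.
- State that the Kaplan-Meier proportion, which counts first occurrences, is not the Week 12 ITCH4 rate.

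Participants "complete and record the Itch NRS via a diary, daily, in the evening beginning on the day of screening" (Protocol 8.2.7.1), so the daily SD and autocorrelation can be estimated from pooled pre-treatment scores without unblinding.

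The cost is SAP wording, one changed derivation and one sensitivity analysis. No new data are needed, since criterion 5 already requires the average. Power falls by at most about 2 points in the settings run (61% to 59%). At low variability fewer events are counted, because a fractional baseline needs a slightly larger whole-number drop: at SD 0.5, smaller effect, autocorrelation 0.3, 54% instead of 62% on active and 27% instead of 34% on vehicle. The trailing event cannot register before about Day 7 and loses up to 6 points of power at SD 0.5 (64% to 58%), so it suits a sensitivity analysis better than the main one.

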7.2.5.2. Skin Pain Numerical Rating Scale

Participants will be instructed to complete and record the Skin Pain NRS in a diary each evening beginning on the day of screening through Week 24 or treatment discontinuation. Participants will rate their pain, which will include all types of pain (eg, burning, tearing, pulling, stabbing, etc) severity of the LS by selecting a number from 0 (no pain) to 10 (worst imaginable pain) that best describes the worst level of pain they experienced in the past 24 hours.

The participant's baseline Skin Pain NRS score will be determined by averaging the 7 daily NRS scores before Day 1 (ie, Days –7 to –1) for all the by-visit summaries. The by-visit Skin Pain NRS score for postbaseline visits will be determined by averaging the 7 daily NRS scores before the visit day. If 4 or more daily scores (out of the 7) are missing, the Skin Pain NRS score at the visit will be set to missing. For all daily skin pain-related analyses, baseline will be defined as the last available Skin Pain NRS score during the week prior to Day 1 (ie, Days –7 to –1). No imputation will be performed for missing values.

l
1
Ī
_

7.3. Analysis of the Primary Efficacy Parameter

7.3.1. Primary Efficacy Analysis

The primary efficacy analysis will be based on the ITT population. The primary efficacy endpoint is the ITCH4 response, defined as a \geq 4-point improvement in Itch NRS score from baseline, at Week 12. The comparison of the proportions of participants with ITCH4 at Week 12 will be made between the ruxolitinib 1.5% cream BID arm and the vehicle cream BID arm. The primary hypothesis (the superiority of ruxolitinib 1.5% cream BID compared with vehicle cream in participants with LS) will be tested using a Chi-squared test at a 2-sided $\alpha=0.05$ level; the p-value will be provided. The Wald 95% CI will be provided for the ITCH4 response rate. A Fisher's exact test will be performed for the comparison if either of the treatment groups has an expected cell count less than 5. Summary of ITCH4 rates will be reported for each treatment group.

All nonresponders in the DBVC period, as well as all participants who are missing Week 12 values, will be defined as nonresponders for the primary analysis.

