6.3. Measures to Minimize Bias: Randomization and Blinding

All participants will be centrally assigned to study treatment using an IRT system. The IRT system will assign a study number to participants and randomize participants to study treatments in a 1:1 ratio. The IRT system will be used to track participant visits, maintain the blinding, and manage study cream inventory. Full details will be provided in the IRT Manual.

Participants, investigators, and the sponsor will be blinded to each participant's treatment assignment during the DBVC period. During the OLE period, participants and investigators will remain blinded to the treatment assignment during the DBVC period. Emergency unblinding will occur if an AE requires the investigator to be made aware of the participant's treatment assignment (see emergency unblinding procedures in Section 9.7 and refer to the IRT Manual).

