3.1. Randomization

Approximately 60 participants will be randomized 1:1 to either ruxolitinib 1.5% cream or vehicle cream BID.

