3.2. Control of Type I Error

The significance level for primary efficacy analysis will be 0.05 for a 2-sided test.

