3.3. Sample Size Considerations

Approximately 60 participants will be randomized 1:1 to ruxolitinib 1.5% cream BID or vehicle cream BID. Due to the lack of data with ruxolitinib cream in LS, the sample size was not calculated based on statistical power calculations, but for demonstration of preliminary findings of clinical response. It is anticipated that a sample size of approximately 60 participants will provide sufficient data to determine whether ruxolitinib 1.5% cream warrants further investigation in LS. Also, the sample size is considered sufficient to provide enough data for the evaluation of the ruxolitinib 1.5% cream safety profile in LS.

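### The primary ITCH4 test is valid but not adjusted for baseline Itch NRS, which gives up some precision and leaves chance baseline imbalance uncorrected in an unstratified trial of about 60

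*SAP*

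**What the plan says.** SAP 7.3.1 compares the two ITCH4 proportions at Week 12 in the ITT population. The hypothesis "will be tested using a Chi-squared test", and for sparse data "A Fisher's exact test will be performed for the comparison if either of the treatment groups has an expected cell count less than 5". On estimation, "The Wald 95% CI will be provided for the ITCH4 response rate"; Protocol 10.4.1 asks for the rate difference with a 95% CI. No covariate or stratum appears in either document. SAP 3.2 adds: "The significance level for primary efficacy analysis will be 0.05 for a 2-sided test".

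On design, SAP 3.1 states: "Approximately 60 participants will be randomized 1:1 to either ruxolitinib 1.5% cream or vehicle cream BID". Under Protocol 6.3 the IRT will "randomize participants to study treatments in a 1:1 ratio", with further detail left to the IRT Manual. Protocol Appendix C (Amendment 1) records that stratification by a baseline score was removed because the trial is small. SAP 3.3 says that "the sample size was not calculated based on statistical power calculations".

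On the endpoint, Protocol 5.1 criterion 5 requires "Baseline Itch NRS score ≥ 4 in anogenital area", taken as a 7-day average with at least 4 days of data. SAP 7.2.5.1 defines response as a fall of at least 4 points on the 0-10 scale. Baseline Itch NRS is tabulated by arm (SAP 6.1.2) and defines a descriptive subgroup split at 7 (SAP 7.3.2). Apart from defining response, it has no other role in the primary analysis.

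**The concern.** A fixed-point responder endpoint builds the baseline into the outcome. A participant who enters near 4 must be almost itch-free for a week to respond, whereas one who enters at 9 may still average 5. Unless Week 12 scores track baseline one-for-one, baseline Itch NRS therefore predicts ITCH4. It is also complete for every eligible participant: criterion 5 needs 4 of 7 days, and the SAP sets a visit score to missing only when 4 or more days are missing, which is the same threshold.

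With about 30 per arm and no stratification, the arms can differ in baseline itch by chance. Neither the design nor the analysis corrects for that. The trial has no power calculation and is meant to show whether the drug warrants further study. A shift of several percentage points in the estimate, or precision given up at no saving, bears on that decision.

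**Working it through.** **Plan's own figure.** There is none to reproduce, since no power, effect size or lichen sclerosus response rate is stated. For context, take one pair of atopic dermatitis ITCH4 rates in Protocol 2.1 (50.7% vs 16.3%) at 30 per arm:
- pooled SE = √(2 × 0.335 × 0.665 / 30) = 0.122
- unpooled SE = √(0.507 × 0.493/30 + 0.163 × 0.837/30) = 0.1135
- power = Φ((0.344 − 1.96 × 0.122)/0.1135) = Φ(0.93) ≈ 82%

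The same formula gives 69% at 50% vs 20% and 35% at 50% vs 30%.

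**Relative fall needed (4 ÷ baseline).** Baseline 4: 100%. Baseline 5: 80%. Baseline 8: 50%. Baseline 9: 44%.

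**Size of chance imbalance.** Assume baseline is normal (mean 6.8, SD 1.5) truncated to 4-10, which leaves an SD of about 1.3. The SD of the between-arm difference in means is 1.3 × √(2/30) = 0.34 points. A gap of 0.5 or more then occurs in 2 × (1 − Φ(0.5/0.34)) ≈ 14% of trials.

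**Simulation.** 30 per arm, 4,000 trials per row. Assumed: mean Week 12 score = 4.6 + slope × (baseline − 6.8), less 2.0 on drug; SD 2.2; clipped to 0-10. Slope 0 means that the Week 12 score is unrelated to baseline, so response depends strongly on baseline. Slope 1 means that response does not depend on baseline. Check at slope 1: vehicle rate = 1 − Φ((4 − 2.2)/2.2) = 0.207 and drug rate = 1 − Φ((4 − 4.2)/2.2) = 0.536, as simulated.

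| Slope | Variance ratio, adjusted/crude | Power: chi-squared / CMH at 7 / standardised logistic | Shift in crude difference per 1-point imbalance |
|---|---|---|---|
| 0 | 0.85 | 64 / 69 / 72% | 13-14 points |
| 0.3 | 0.93 | 70 / 72 / 74% | 8-10 points |
| 0.6 | 0.98 | 75 / 76 / 76% | 5-7 points |
| 1.0 | 1.01 | 76 / 77 / 77% | 0 |

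The Monte Carlo SE of a power figure is about √(0.64 × 0.36/4,000) = 0.8 points.

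Cross-check at slope 0: a 1-SD imbalance moves the estimate by 0.34 × 14 = 4.8 points, against a crude SD of 11.9 points. Its share of the variance is (4.8/11.9)² = 0.16. That agrees with the 15% reduction, after about 1% for the extra parameter. A 2-SD imbalance moves the crude difference by 0.68 × 14 ≈ 9.5 points. After adjustment the shift is 0.5 points or less per half-point of imbalance.

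**Second model.** Itch falls in proportion to baseline; baseline is normal (6.5, 1.5) truncated to 4-10. With strong baseline dependence, chi-squared/Fisher, CMH and a linear model with HC3 standard errors gave 82.9, 85.9 and 87.4% power at 50.7% vs 16.3%, and 52.1, 56.0 and 57.9% at 50% vs 25%. Across runs under proportional reduction, the shift per 1-point imbalance was 6-14 points. With response unrelated to baseline, the variance ratio was 1.01-1.02 and power fell by up to about 1 point.

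**Null rejection at 30 per arm (nominal 5%):**
- planned rule: 3.2-5.2%
- CMH at 7: 4.5-5.1%
- linear model with HC3: 4.0-4.9%
- standardised logistic with small-sample correction: 4.3-5.6%
- standardised logistic with uncorrected robust SE: 5.1-6.7%

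**The case against.** The strongest reply is that nothing here is invalid. A chi-squared test of two randomised proportions holds its level, and its p-value and CI already allow for chance baseline differences on average over randomisations. The trial claims no power, so no target is missed. The gain is modest, model-dependent, and nil if Week 12 scores track baseline. An imbalance would be visible in the baseline table and the subgroup summaries. The obvious replacement, a standardised logistic risk difference with an uncorrected robust SE, would exchange a test that holds alpha for one that can exceed 5% at this size. Changing the test also departs from Protocol 10.4.1.

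Most of that stands. It rules out some stronger readings that a reader might infer:
- That type I error is inflated. It is not. At slope 0, among null trials in which the drug arm was at least 0.5 points higher at baseline, false positives favouring drug were about 10% crude and 3% adjusted (nominal 2.5%). That is conditional on an imbalance, rests on a few hundred trials, and largely disappears at higher slopes.
- That low-baseline participants cannot respond. They can, but they need a larger relative fall.
- That randomisation is simple, or that the dropped stratification factor was itch. The documents only show that it is unstratified. Blocking is not described, and the public text does not name the score.

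Three parts do not stand. Descriptive tables can reveal an imbalance but do not correct the test or the CI. A small sample is a reason to drop strata at randomisation, but not to leave out one covariate in the analysis. The alpha problem belongs to one form of adjustment; the other methods listed stay at about 5%.

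**Conclusion.** The point holds as one of precision and of imbalance left uncorrected in the estimate. The planned analysis is valid, but it ignores a complete and probably prognostic baseline value.

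Under the assumed models the variance ratio is about 0.85 to 1.02. At 0.85, an adjusted analysis of 60 has the precision of 60/0.85 ≈ 70 unadjusted. Power gains run from 0 to about 8 points. The top value comes from the standardised logistic analysis, whose null rejection in those same runs was 5.1-5.9%, so part of it may reflect a slightly liberal test. In the strong-dependence settings shown, CMH and the HC3 model, which hold alpha, gained about 3 to 6 points. Each 1-point baseline imbalance shifts the crude difference by 0 to about 14 points.

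All of this depends on assumed baseline distributions, outcome SDs and response rates; the documents give none for lichen sclerosus. The change is worth making because it is cheap, not because the planned result would be unsound.

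**What to change.** Before the primary database lock and unblinding, amend SAP 7.3.1 so that the primary ITCH4 analysis is baseline-adjusted, and name one method:
- a CMH test with a stratified risk difference and 95% CI, with strata <7 and ≥7. The categories in SAP 7.3.2 as printed both include 7, so the cut must be settled; or
- a risk difference adjusted for continuous baseline Itch NRS, with a small-sample-corrected robust SE (for example HC3, or a degrees-of-freedom correction with a t reference). An uncorrected sandwich Wald test should not be used.

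Keep the crude chi-squared/Fisher result as supportive and as the fallback if the model does not converge. State how a randomised participant without a valid baseline score is handled. Record the departure from Protocol 10.4.1 in SAP 11.1, which now lists no changes.

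The cost is a short SAP amendment with that declared change, and no new data. If baseline proves not to be prognostic, up to about 1 power point is lost.
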